#### 4.5 Frozen section technique (NeuroSAFE).

The NeuroSAFE technique was developed at the Martini Klinik in Germany. NeuroSAFE has been shown to increase the rate of nerve sparing and reduce the rate of PSM at RARP in observational studies. Currently, almost all patients treated with nerve sparing radical prostatectomy at the Martini Klinik undergo a NeuroSAFE procedure. However, the procedure is relatively costly as it is labour intensive and requires a consultant pathologist to examine the sections. (1)

The technique itself does not result in a significant increase in operative time. This is because the specimen is extracted immediately when it is detached from the adjacent tissues and sent for frozen section analysis. Whilst this analysis is underway, the lymphadenectomy and fashioning of the urethro-vesical anastomosis can be performed. With this technique >99 % of pathologically organ-confined cancers and >90% of capsular-penetration (pT3a) or seminal vesicle (pT3b) invading tumours can be offered a nerve-sparing procedure, while reducing the rate of positive margins at the dorsolateral aspect to <1% and by more than 50% overall. If a posterolateral positive surgical margin is detected, resection of the NVB has been shown to result in oncological outcomes similar to if a negative surgical margin had been achieved in the first place. (24)

A further modification of the NeuroSAFE system has been developed and piloted at the Lister Hospital in Stevenage by the collaborators on this project. The Lister

Hospital is currently the only UK centre offering frozen section analysis of the neurovascular bundles routinely, outside of this trial.

A systematic review has been performed by our group on intra-operative frozen section (IFS) evaluation of the prostate margin during RP. Medline, EMBASE and the Cochrane Library were systematically searched without time nor language limitations (CRD4201912594). Ten non-randomized comparative studies (including 16, 897 patients) were retrieved. According to risk of bias assessment, seven studies suffer from serious risk of bias, whereas three studies suffer from moderate risk of bias. Performance of IFS greatly differed technically between studies. Eight studies report a reduction in rates of PSM (-1.4% to -14.5%) with the use of IFS and two studies report higher PSM rates (+0.4% to +10%) in IFS group. Four studies that perform IFS systematically at the posterolateral margin of the prostate all report either improved NVB preservation or improved erectile function (EF) recovery. Our groups' conclusions included that, no RCTs were identified, and most included studies are at high risk of bias. Furthermore, only very few of the studies included results on either long term oncological or functional outcomes. Within the limitations of this review, the evidence suggests that IFS during RP can modestly reduce PSM rates. IFS performed systematically at the posterolateral margin of the prostate (the NeuroSAFE technique) can facilitate more NVB preservation, which may contribute to improved patient functional outcome recovery, though this has not been proven in prospective studies yet. In short, randomized, prospective, standardized research with long term oncological and functional outcomes are lacking to date. We feel this further strengthens the case for the conduct of the NeuroSAFE PROOF trial.

## 5 HYPOTHESES & OBJECTIVES

### 5.1 Hypotheses

- Men undergoing NeuroSAFE RARP will experience superior EF recovery compared to men undergoing standard RARP.
- Men undergoing NeuroSAFE RARP will experience improved recovery of urinary continence at 3 months following surgery compared to men undergoing standard RARP.
- Men undergoing NeuroSAFE RARP will experience the same rates of cure from surgery compared to those undergoing standard RARP.

## 6 Objectives

### 6.1 Primary

To assess the difference in erectile function recovery between men undergoing standard RARP (control arm) and NeuroSAFE RARP (intervention arm) at 12 months following treatment using the IIEF-5 questionnaire.

### 6.2 Secondary

1. To evaluate the differences in urinary continence recovery in the early period following treatment (3 and 6 months) between men undergoing standard RARP (control arm) and NeuroSAFE RARP (intervention arm).
2. To evaluate the differences in oncological outcomes (including BCR and administration of adjuvant/salvage treatments) between men undergoing standard RARP vs. NeuroSAFE RARP at 12 months. Additional analysis is intended at 5 years post-surgery.
3. To evaluate differences in overall quality of life outcomes between men undergoing standard RARP vs NeuroSAFE RARP at 12, 24, 36, 48 and 60 months after surgery and a maximum frequency of annually thereafter.
4. To evaluate differences in recovery of erections after 12-months and up to 2 years between men undergoing standard RARP vs NeuroSAFE RARP
5. Economic analysis to assess health resource use between standard RARP vs NeuroSAFE RARP at 12 months and up to 2 years post treatment.

---

 Evaluation after 12 months dependent on future funding

## 7 TRIAL DESIGN

### 7.1 Type of Trial

A single blinded, IDEAL stage 3, multi-centre, randomised controlled trial to assess NeuroSAFE Robotic assisted radical prostatectomy (RARP) vs standard RARP in men with prostate cancer. Men will be randomised 1:1 to NeuroSAFE RARP (intervention arm) vs Standard RARP (control arm). This trial aligns with an IDEAL framework Stage 3 Assessment for the evaluation of complex surgical interventions.

### 7.2 Outcome endpoints

#### 7.2.1 Primary

Comparison of the proportion of men who recover erectile function at 12 months allocated to the NeuroSAFE intervention versus the control arm. Erectile function is measured using the IIEF-5 patient reported outcome questionnaire, where recovered function is defined as a score of 21 or more.

#### Patient Answers to the IIEF-15

- Patients should be made aware before filling in their follow-up visit questionnaire responses, that oral medications such as PDE5 inhibitors (e.g. sildenafil, tadalafil and others of the same class) will be permitted when taking into account the strength of erection achievable during intercourse or sexual stimulation.
- For the purposes of answering the IIEF-15 questions, erections achieved with the assistance of ancillary erectile aids such as the vacuum pump, intra-cavernosal injections, penile creams and prostheses should not be considered in the answers. The reason for this division is that the ancillary erectile aids (pumps, injections) are not related to cavernosal nerve preservation (NS RARP) and therefore the inclusion of these devices in the answers would introduce confounding.
- Erectile function will also be assessed, including use of erectile function aids by the additional erectile function questionnaire CRF.

#### Verbal questionnaire responses (telephone)

- Since the Covid-19 Pandemic and government restrictions on movement including hospital appointments, the NeuroSAFE PROOF team have been conducting trial follow-up visits via telephone. All trial questionnaires have been sent to participants in the post. In order maintain data completeness on key outcome measures (such as erectile function at 12-months [IIEF-15] and urinary continence at 3 months [ICIQ]), the trial clinical team have been administering these PROM questionnaires over the telephone.

- As of protocol version 5.0, to ensure data completeness and to avoid submitting repeated protocol deviations for each instance, this method of data capture is now an accepted method of data collection. Any paper copies returned by post will supersede verbal responses.
- In order to distinguish between source data origins, a new electronic CRF database will have the facility to record whether PROM items were obtained by paper questionnaires submitted by post, electronic versions submitted following email reminders, or verbally with a clinician over the telephone.

Further planned analyses:

- Additional subgroup analysis: restricted to men who did not receive a pre-operative radiologist recommendation for bilateral nerve sparing.
- Additional subgroup analysis: patients who did not receive adjuvant treatment (adjuvant therapy defined as any additional treatment without a  $PSA > 0.2 \text{ ng/ml}$ ).
- Sensitivity analyses: additional analysis at 12 months
  - (a) IIEF-5 using a threshold  $\geq 15$
  - (b) IIEF-5 using a threshold of  $\geq 2$  for question 3
- Descriptive analysis of IIEF-5 at 3-, 6-, 12- and 24-months post-surgery

## 7.2.2 Secondary Endpoints

### 7.2.2.1. Urinary Continence

Comparison of the proportion of men who are continent at 3 months, measured using the ICIQ PROM, where continence is defined as a score of 5 or less, between the NeuroSAFE RARP arm and the standard RARP arm.

- Sensitivity analyses: Analysis of incontinence at 6 months ICIQ score of 5 or less
- Additional subgroup analysis: restricted to men who did not receive a pre-operation radiologist recommendation for bilateral nerve sparing.
- Additional subgroup analysis: patients who did not receive adjuvant treatment (adjuvant therapy defined as any additional treatment without a  $PSA > 0.2 \text{ ng/ml}$ )
- Descriptive analysis of ICIQ scores at 3-, 6-, 12- and 24-months post-surgery

---

 Analysis after 12 months dependent on future funding

 Analysis after 12 months dependent on future funding

#### 7.2.2.2. BCR

Comparison of the proportion of men with BCR between NeuroSAFE and control arms within 12 months of surgery. BCR will be considered to have occurred when the post operative PSA measures  $>0.2$  ng/mL, or where the PSA level is less than 0.2 ng/mL but the trajectory suggests inevitable rise above 0.2 ng/mL according to the clinician looking after the patient. If PSA fails to nadir after surgery, this will not be considered BCR as this is probably related to micro metastatic disease not detected by preoperative imaging. Patients with demonstration of metastases on imaging will not be considered as BCR for the same reason.

- Follow up time of 12 months is defined as cumulative time up to the 12-month visit. Patients visits after more than 13.5 months post-surgery will not be included (12 months + 6 weeks max visit window).
- Additional descriptive analysis will report recurrences across all patients at the following times: Within 3 months (+/- visit window) and within 6 months (+/- visit window).
- Descriptive analysis of BCR for each arm according to
  - (a) Gleason grade
  - (b) TNM stage
  - (c) pre-operative PSA level
  - (d) routinely used risk classifiers (D'Amico, CAPRA, EAU) (e) time of recurrence.

If patients have a low but detectable PSA level the frequency of testing would be increased from the usual schedule (3,6,9,12 months) depending on the trajectory and level of concern of the clinician looking after the patient.

#### 7.2.2.3. Additional oncological treatments

For men who receive additional cancer treatment, despite not having reached a PSA threshold of  $PSA > 0.2$  ng/ml post-surgery will be considered as having undergone 'adjuvant treatment.' Descriptive analysis of proportions of men undergoing adjuvant oncological treatments at or before 12 months of surgery, including tabulating the types of treatment that these men underwent. Reasons for adjuvant treatment (i.e. before BCR) will be documented where possible.

Men who receive additional cancer treatment, following a PSA at or above the threshold of  $PSA > 0.2$  ng/ml post-surgery will be considered as having undergone 'salvage treatment.' Descriptive analysis of proportions of men undergoing salvage oncological treatments at or before 12 months of surgery, including tabulating the types of salvage treatment that these men underwent.

#### 7.2.2.4. Quality of life

Comparison of the proportion of men's quality of life on NeuroSAFE intervention compared to control arm.

- Analysis of EQ-5D-5L scores to produce QALYs at 12 months by arm
- Analysis of RAND36 scores to produce QALYs at 12 months by arm
- Analysis of EPIC-26 scores to produce QALYs at 36-, 48-, and 60 months and a maximum frequency of annually thereafter by arm

Graphical presentation and descriptive analysis of RAND36 and EQ-5D-5L at 3-, 6-, 12- and 24-months post-surgery.

#### 7.2.2.5. Positive Surgical Margins (PSM)

Descriptive tabulation of PSM rates between NeuroSAFE RARP and standard RARP arms. PSM will be grouped as:

0. Negative margin
1. Intraprostatic margins
2. Non-intraprostatic margins  $\leq$  1mm (included)
3. Large non-intra prostatic margins and  $>$  1mm
4. Very large non-intraprostatic margins and  $>$  3mm and/or multifocal

[figure not shown]
Additional subgroup analysis: restricted to men who did not receive a pre-operative radiologist recommendation for bilateral nerve-sparing.

#### 7.2.2.6. Health Economic Analysis

Use of the Health Resource Questionnaires to inform a health cost analysis of NeuroSAFE RARP vs. standard RARP. Please see section 11.3.

- Descriptive analysis by arm
- Economic analysis to assess healthcare resources use by arm and cost analysis to assess:
  - Cost of intervention and control
  - Cost of NHS resource use (medications, physiotherapy)
  - Cost of private health care resources (medication, physiotherapy)
  - Other private/societal costs (productivity losses, caregivers costs, out of pocket cost for transport, equipment)

### 7.3 Trial Schedule

NeuroSAFE Protocol Version 7.0 dated 14 February 2023  
IRAS Reference Number 220262

## 7.4 Table of Assessments

Visit	Screening/ Baseline	Randomisation	Treatment Visit 1	Visit 2 3 months ( $\pm 6$ weeks)	Visit 3 6 months ( $\pm 6$ weeks)	Visit 4 12 months ( $\pm 6$ weeks)	Visit 5  2 years ( $\pm 6$ weeks)	Visit 6 3 years ( $\pm 6$ weeks)	Visit 7 4 years ( $\pm 6$ weeks)	Visit 8 5 years ( $\pm 6$ weeks)	After Visit 8**
Informed consent	x										
Randomisation		x									
Fitness for surgery assessment	x										
PSA	x			x	x	x	x	x	x	x	x
Standard care referral pathway to regional uro-oncology centre	x										
MRI guided pre-op surgical planning			x								
RARP (standard/control or NeuroSAFE/intervention)			x								
Adverse events	x	x	x	x	x	x	x				
EQ-5D-5L – (P/C/E/T)*	x			x	x	x					
ICIQ – (P/C/E/T)*	x			x	x	x					
IIEF-5 – (P/C/E/T*)	x			x	x	x					
RAND36 – (P/C/E/T)*	x			x	x	x					
Additional Erectile Function (EF) questionnaire (P/C/E/T)*				x	x	x					
Additional Treatments Assessment				x	x	x	x	x	x	x	x
Health Resource Diaries data collection				x	x	x	x				
RAND36, IIEF, EQ-5D-5L, ICIQ and Additional EF questionnaire – (P/E/C/T)							x				
EPIC-26 questionnaire (P/E)*								x	x	x	x

\*P – Postal, E – Email, C – Clinic, T - telephone

\*\* after visit 8 data to be collected for a maximum frequency of annually

 Visits after 12 months dependent on future funding

## 8 TRIAL ELIGIBILITY

### 8.1 Number of sites

This trial will be run as a multi-centre, IDEAL stage III trial. There will be a combination of recruiting centres and participant identification centres (PIC sites).

### 8.2 Inclusion criteria

1. Men opting to undergo RARP for organ confined prostate cancer (including radiological t3a).
2. Potent men (IIEF score of 22-25 not using PDE5i or other medications or devices for first 5 questions at baseline (from baseline PROM or clinical notes)
3. Men who are continent of urine (no self-reported urinary incontinence)
4. Has given written informed consent
5. Ability to read English sufficiently to answer questionnaires and understand PIS

### 8.3 Exclusion criteria

1. Unable to undergo robotic prostatectomy
2. Known overactive bladder
3. Previous treatment for prostate cancer
4. Previous/current hormone treatment for prostate cancer
5. Nerve sparing deemed futile due to locally advanced disease by surgeon and radiologist

### 8.4 Withdrawal criteria

1. Unable to perform nerve sparing as planned due to anatomical/technical difficulty during surgery. Intention to treat analysis will be undertaken
2. Patient changes their mind

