## 2 TRIAL OVERVIEW

Trial Title	A single blinded, IDEAL stage 3, multi-centre, randomised controlled trial to assess NeuroSAFE Robotic assisted radical prostatectomy (RARP) vs standard RARPs in men with prostate cancer
Short Title	NeuroSAFE at prostatectomy to optimise oncological and functional outcome. (NeuroSAFE PROOF)
Aim	This is an RCT to assess the differences in functional and oncological outcomes between RARP using the NeuroSAFE intraoperative frozen section technique to navigate safe nerve sparing and standard UK practice RARPs
Inclusion criteria	
 
1. Men opting to undergo RARP for organ confined prostate cancer (including radiological t3a).
 
2. Potent men (IIEF score of 22-25 without any erectile function medical assistance)(from baseline PROM or clinical notes)
 
3. Men who are continent of urine (no self-reported urinary incontinence)
 
4. Has given written informed consent
 
5. Ability to read English sufficiently to answer questionnaires and understand PIS
 

Exclusion criteria	
 
1. Unable to undergo RARP
 
2. Known overactive bladder
 
3. Any previous treatment for prostate cancer
 
4. Previous/current hormone treatment for prostate cancer
 
5. Nerve sparing deemed futile due to locally advanced disease by surgeon and radiologist
 

Withdrawal criteria	
 
1. Unable to perform nerve sparing RARP as planned due to anatomical/technical difficulty during surgery
 
2. Withdrawn consent
 

Trial procedures	
Control arm - standard RARP:
 
Nerve-sparing strategy during RARP guided by routinely available pre-operative and intra-operative patient/disease information; mpMRI, biopsy tumour histology, DRE.
 
Intervention arm – NeuroSAFE RARP:
 
Nerve-sparing strategy during RARP guided by routinely available pre-operative and intra-operative patient/disease information; mpMRI, biopsy tumour

	histology, DRE and the NeuroSAFE technique during RARP.

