### 9.2 Screening and Consent

After a potential participant has had sufficient time to read the PIS, the enrolment process will follow these steps:

- The purpose of the research and the trial procedure is outlined again to the participant to ensure they understand. If the subject is willing to proceed, the participant will be asked to sign the approved trial consent form. This form may be a hard copy or an electronic consent form sent via an NHS account to the participants email. The original signed consent form will be filed in the investigator site file (ISF) after co-signature by an appropriate member of the research team. A copy will then be given to the participant and a copy filed in the hospital case notes. In the case of an electronic consent form, once signed and sent back to the research team, a fully co-signed copy is sent back to the participant, a copy is printed and stored in the ISF and a copy is stored in the hospital case notes. Please see section 9.3 for further details on e-consent.
- If the participant is willing to take part in the trial, eligibility to enter the trial is assessed based on inclusion and exclusion criteria. If all trial criteria are met, the screening visit CRF is completed. If a participant declines, this is also recorded in the screening log. A unique screening number will be assigned to participants recorded on the screening log.
- The participant is deemed to be recruited into the trial and the participant's GP is informed. At this point a unique subject trial number is allocated.
- Using the Sealed Envelope randomisation system, the patient is randomised using their allocated trial number and will be assigned to either the control or intervention arm. They will then be informed of their date for surgery.

- The patient will be blinded as to which arm they are randomised to. The surgeon will not be blinded. Unblinding will only be performed if an adverse event occurs where knowledge of allocation is perceived by the PI to be important in determining ongoing management.

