#### 10.1.1 Control Arm: Standard RARP

Standard RARP (control arm) is performed as per NHS routine practice at participating regional uro-oncology sites. Pre-operative parameters used to guide surgeon Nerve Spare (NS) decision include mpMRI NS planning sheet prepared in conjunction with a consultant genito-urinary radiologist, prostate biopsy tumour histology information and digital rectal examination under general anaesthesia. Individual surgeons are asked after RARP to grade the quality of NS performed on each side numerically as seen below (25):

- Grade 0 - No nerve spare. Wide excision of lateral pelvic fascia (LPF) and Denonvilliers' fascia.
- Grade 1 - Limited nerve spare, or partial/incremental nerve spare. Incision through outer compartment of LPF.
- Grade 2 – Interfascial nerve spare. LPF is taken just outside the layer of the veins of the prostate capsule. Still largely preserving the large neural trunks (also known as the NVBs).
- Grade 3 – Intrafascial nerve spare. LPF is taken just outside the prostate capsule. Represents greatest possible NS.

NeuroSAFE PROOF collects detailed information on histological surgical margin status for safety and future publication purposes. Descriptions of histological diagnosis can differ between sites due to varying interpretations of histological analyses. In line with quality assurance, we will request anonymised pathology reports to ensure accurate, standardised reporting in the trial database. This will occur across both arms of the trial.

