#### 10.1.2 Intervention Arm: NeuroSAFE RARP

NeuroSAFE RARP (intervention arm) will be performed in accordance with previously described methods, initially developed at the Martini Clinik, Hamburg, Germany. All patients in the NeuroSAFE arm will undergo initial bilateral NS where technically possible. The procedure differs from standard RARP in that initial insertion of the robotic camera port is through a modified incision using the Alexis Laparoscopic System (Applied Medical, Rancho Santa Margarita, CA).

Once the specimen is disconnected from its attachments, the specimen can be removed from the patient through the protected incision immediately.

Pneumoperitoneum can be re-established quickly by placing the laparoscopic cap back on the Alexis.

The specimen will then be painted by the operating surgeon (sites may differ, but at UCLH; yellow for left and green for right side of the prostate). The painted areas can be sprayed with a fixative spray if site prefers (to prevent ink running). The specimen will be delivered expediently to the pathology laboratory where frozen section analysis of the painted areas will be undertaken. Whilst this analysis is taking place the robot will be re-docked and pneumoperitoneum established. The robotic instruments will be reinserted. The surgeon will proceed to fashion the urethro-vesical anastomosis and perform a pelvic lymphadenectomy (where indicated) whilst the result of the frozen section analysis is awaited.

Upon delivery of the prostate gland to the pathology lab, a sharp blade will be used to remove the pre-painted surface of the gland (which had been in contact with the neurovascular bundles). The tissue sample will be snap frozen and embedded in OCT. Using a cryostat, 10-micron thick slices will be placed on slides. The entire length of the area of interest will be sampled in this way generating an average of 5 frozen sections per side and approximately 10 in total. The slides will be stained with H&E and will be examined by a consultant pathologist. As soon as examination is complete the pathologist will telephone the operating surgeon to give the result. On frozen section analysis, presence of cancer cells at the inked surface margin of the specimen constitutes a positive margin and the length of any positive surgical margin will be recorded.

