##### **Inter-current illness**

Any illness, which in the judgment of the investigators would affect the assessments of clinical status to a significant degree

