4.7 Primary outcome analysis

The primary estimand of interest will be the difference in mean IIEF-5 score at 12 months between participants allocated to the NeuroSAFE and those allocated to the standard treatment group among those who received the surgery.

The primary outcome (the IIEF-5 score at 12 month) will be analysed using a normal linear regression model. The model will include randomisation group, site (the stratification variable), age, and IIEF-5 at baseline. Continuous covariates (age and IIEF-5) will be included as a linear term, while site will be included as categorical. The estimated coefficient for the adjusted mean difference between randomisation groups will be presented alongside its 95% confidence interval and two-sided p-value

The primary analysis will include everyone in the mITT population with IIEF-5 available at 12 months.

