4.10.3 Subgroup analysis within the non-BNSR participants

We will compare outcome between the NeuroSAFE and standard arm, within the subgroup of participants where bilateral nerve sparing was not recommended.

We will estimate the difference in the primary (IIEF-5 at 12 month) and the main secondary (ICIQ at 3 months) outcomes between arms in this subgroup, using the same analysis model specified in section 4.7 and 4.8 (linear regression adjusted for age, site and baseline IIEF-5 or ICIQ) but restricted to participants without BNSR.

We may also report (without formal testing) on the difference in other secondary and descriptive outcomes within this subgroup, if appropriate.

Although this subgroup analysis may be less powered than the primary analysis of the trial, we expect around 2/3 of the trial participants to belong to this subgroup. This sample size should be sufficient power to detect moderate or large difference between arms.

We will not compare the outcomes within the converse subgroup (participants for whom bilateral never sparing was recommended), which would be of lesser relevance and likely to lack statistical power.

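### Failure to spare nerves as planned is listed as a withdrawal criterion without saying that follow-up continues; if it stops, likely poor outcomes leave the primary analysis, possibly unequally by arm

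*Protocol*

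**What the plan says.** Protocol 8.4 gives two withdrawal criteria. The first is "Unable to perform nerve sparing as planned due to anatomical/technical difficulty during surgery. Intention to treat analysis will be undertaken". The second is that the patient changes his mind. The overview (Protocol 2) lists "Unable to perform nerve sparing RARP as planned due to anatomical/technical difficulty during surgery" beside withdrawn consent and says nothing about intention to treat.

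The nerve-sparing plan is set differently in each arm. For the intervention, Protocol 10.1.2 says "All patients in the NeuroSAFE arm will undergo initial bilateral NS where technically possible". For control, Protocol 10.1.1 says "Pre-operative parameters used to guide surgeon Nerve Spare (NS) decision include mpMRI NS planning sheet", together with biopsy histology and rectal examination. On who knows the allocation, Protocol 9.2 says "The surgeon will not be blinded".

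On analysis, the SAP 4.1.1 modified ITT set keeps every randomised man who had either operation. SAP 4.7 then narrows this: "The primary analysis will include everyone in the mITT population with IIEF-5 available at 12 months". SAP 4.1.2 assumes outcomes are missing at random given arm and baseline covariates. SAP 4.11.2 adds a not-at-random sensitivity analysis in which men with no IIEF data after surgery start from the lowest score at visit 2.

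Protocol 13.1.2 adds another exit, for intercurrent illness: "Any illness, which in the judgment of the investigators would affect the assessments of clinical status to a significant degree".

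**The concern.** Being unable to spare a nerve is a result of the operation, and it lies on the path to the primary outcome. The protocol's own figures show how strongly. Section 3.1 reports usable erections in 85% of men after bilateral sparing and 45% after unilateral sparing, at 2 years with a PDE5 inhibitor. Section 4.1 reports erectile dysfunction in 95% after non-nerve-sparing surgery.

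If meeting the criterion ends a man's follow-up, the men lost are those expected to do badly. The arms may also lose different numbers. The NeuroSAFE plan starts from both sides, whereas the control plan often will not: SAP 4.10.3 says of men without a bilateral recommendation that "we expect around 2/3 of the trial participants to belong to this subgroup". More planned sides give more chances to fail the plan.

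The primary model adjusts for site, age and baseline IIEF-5 but not for nerve-sparing result, so it cannot correct for loss that depends on that result. Continence and PSA follow-up on the same men would also be lost.

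**Working it through.** **1. Does the rule remove men from the primary analysis?**

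- No analysis-set definition excludes them. Protocol 12.2.1 counts all consenting men and SAP 4.1.1 counts all operated men.
- The primary analysis nevertheless needs an observed 12-month IIEF-5 (SAP 4.7). A man whose follow-up ended stays in the modified ITT set by definition but contributes nothing to the estimate.
- Protocol 12.2.5 supported ITT with multiple imputation from all time points. The SAP main analysis uses available data instead.
- The only instruction to keep following a man who meets an exit criterion is in Protocol 13.1.2, for men who stop attending the site.

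The result therefore turns on what withdrawal means, which is undefined.

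**2. The plan's own figure.** SAP 1.4 has 42% vs 28%, 80% power, two-sided 5%:

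n per arm = [1.96·√(2·0.35·0.65) + 0.842·√(0.28·0.72 + 0.42·0.58)]² / 0.14² ≈ 181.0, rounded up to 182, so 364 evaluable. Then 364/0.9 = 404.4, against 404 stated. This reproduces.

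**3. Bias if there is no true effect (28% in both arms).** Let w be the share withdrawn and lost, and r their recovery rate. The rate among retained men is (p − w·r)/(1 − w). The documents give no w, so the values are assumptions. I take r = 0 to 5%, the upper end from Protocol 4.1.

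| Control / NeuroSAFE withdrawn | r | Retained control | Retained NeuroSAFE | Bias (points) | Two-sided rejection |
|---|---|---|---|---|---|
| equal | any | same | same | 0 | 5.0% |
| 1% / 5% | 0 | 28.3% | 29.5% | +1.2 | 5.7% |
| 1% / 5% | 5% | 28.2% | 29.2% | +1.0 | 5.5% |
| 2% / 10% | 0 | 28.6% | 31.1% | +2.5 | 8.1% |
| 2% / 10% | 5% | 28.5% | 30.6% | +2.1 | 7.1% |

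Swapping the arms reverses the sign. If the true rates are 42% and 28%, even equal withdrawal of 5% per arm widens the difference by 0.7 points.

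**4. Distortion of the 14-point difference from a per-side failure chance q.** Assumptions:

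- The NeuroSAFE plan is always bilateral.
- The control plan is 40% bilateral, 40% unilateral and 20% none. The 40% bilateral is the 2018 figure for all such operations at one centre (Protocol 4.4). The rest of the split is assumed.
- Retained men recover at 42% and 28%.
- A man planned for bilateral sparing who fails on one side recovers at 45/85 of his arm's rate: 0.42 × 45/85 = 22% for NeuroSAFE and 0.28 × 45/85 = 15% for control. As a range, control is also run at 22%.
- A man left with no nerve spared recovers at 5%.

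Withdrawn: NeuroSAFE w1 = 1 − (1 − q)²; control w0 = 0.4·w1 + 0.4·q.

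Overstatement = [2q(1−q)(0.42−0.222) + q²(0.42−0.05)] − [0.4·2q(1−q)(0.28−c) + (0.4q² + 0.4q)(0.28−0.05)], with c = 0.148 or 0.222.

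| q | Withdrawn, NeuroSAFE / control | Men of 364 | Overstatement (points) | True difference (points) |
|---|---|---|---|---|
| 2% | 4.0% / 2.4% | about 12 | 0.4–0.5 | 13.6–13.5 |
| 5% | 9.8% / 5.9% | about 28 | 1.0–1.3 | 13.0–12.7 |

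At q = 10% the model would withdraw 19% of the NeuroSAFE arm, nearly twice the planned 10% total drop-out, so I do not rely on it.

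**5. On the SAP's scale.** SAP 4.7 compares mean IIEF-5. If withdrawn men would have scored g points below retained men, bias = g·(w_NeuroSAFE − w_control). For an assumed g of 5 to 10 points, 1% vs 5% gives 0.2–0.4 IIEF-5 points and 2% vs 10% gives 0.4–0.8.

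**The case against.** The strongest reply is that the documents never say withdrawal ends follow-up. The ITT remark is attached to this criterion and not to the patient changing his mind, which makes most sense if these men are to be kept. Withdrawal might also mean only from the allocated procedure, since in the NeuroSAFE arm the frozen-section step comes after sparing. This stands as far as it goes: loss of these men is a risk and not an established fact. But the criterion sits beside withdrawn consent, the overview omits the ITT remark, and an ITT intention cannot supply an outcome that nobody collected.

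A reader might infer that the rule must drop more men from the NeuroSAFE arm and so favour it. The documents do not support that. Bilateral sparing there applies where technically possible, so an impossible side could still count as planned. Protocol 10.2 leaves sparing in both arms to the surgeon's discretion. Bundle resection after a positive frozen section (Protocol 10.1.2) is part of the procedure, not a technical difficulty, and should not trigger the criterion. No rates by arm are given.

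A reader might also give every withdrawn man 5% recovery, which puts the overstatement at q = 5% at 2.2 points. That figure belongs to non-nerve-sparing surgery, while most NeuroSAFE failures in the model lose one side only. Allowing for this roughly halves the result.

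Finally, SAP 4.11.2 does cover a man lost at surgery, and SAP 4.2 already reports reasons for withdrawal by arm. Both help, but the first is only a sensitivity analysis and the second only describes the loss.

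**Conclusion.** The point holds as a conditional one. A stated withdrawal rule, read in its natural sense, would create outcome-related missing data in the primary analysis and contradict the ITT promise in the same line. Nothing in either document tells sites to read it otherwise.

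The size is modest and rests wholly on assumed withdrawal rates: about 0.4–1.3 points on the 14-point difference for 2–5% failure per planned side, and about 1–2.5 points in either direction under no effect for the imbalances shown. It is zero if the men are followed up.

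Intercurrent illness in Protocol 13.1.2 is a weaker, separate matter. It has the same gap about continued outcome collection, but there is no argument that it differs by arm.

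**What to change.** - In Protocol 8.4 and section 2, remove this event from the withdrawal criteria. Record it as an intra-operative departure, using the per-side nerve-sparing grade (0–3) already collected.
- State that the man stays in the trial for all IIEF, ICIQ and PSA visits and is analysed in his allocated arm.
- In the SAP 4.2 flowchart, report the number of such men by arm. For any already withdrawn under the rule, retrieve 12-month outcomes where consent allows.
- In Protocol 13.1.2, state that outcome collection continues after intercurrent illness unless the patient withdraws consent.

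The cost is protocol wording and some extra questionnaires to chase among men already consented. No surgical decision changes, and the 364 evaluable and 404 recruited stand.
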